### 17.1 Sample size calculation

The primary objective of this trial is to confirm efficacy of IDegAsp 30 BID ± metformin in terms of glycaemic control.

This is done by showing that:

IDegAsp 30 BID ± metformin is non-inferior to BIAsp 30 BID ± metformin in terms of glucose lowering effect as assessed by change from baseline in HbA1c after 26 weeks of treatment using a non-inferiority margin of 0.4% (absolute). Sample size is determined based on this primary objective.

Throughout this section of the protocol the term “investigational product” will be used as a synonym for IDegAsp 30 and the term “comparator” will be used as a synonym for BIAsp 30 BID.

The non-inferiority margin of 0.4% (absolute) was chosen in accordance with the FDA guidance. Let D be the mean treatment difference for change in HbA1c (investigational product minus comparator). The null-hypothesis will be tested against the alternative hypothesis of non-inferiority as given by

$H_0: D > 0.4\%$  against  $H_A: D \leq 0.4\%$

Operationally the null-hypothesis will be rejected and non-inferiority considered confirmed if the upper bound of the two-sided 95% confidence interval for the mean HbA1c treatment difference is below or equal to 0.4%. This is equivalent to using a one-sided test of size 2.5%.

Sample size is determined using a t-statistic under the assumption of a one-sided test of size 2.5% and a zero mean treatment difference (i.e. D=0%). Based on experience from previous phase 3 trials in subjects with type 2 diabetes treated with insulin an estimate for the standard deviation (SD) of 1.3% for HbA1c will be used in the sample size calculation ([Table 17-1](#)). The sample size calculation is done using SAS 9.3.

**Table 17-1 Specifications assumed for sample size calculation**

Statistical test	One sided Significance Level	Non-inferiority Margin	SD	Mean Difference	Randomisation Scheme	Required Power
two-group t test	2.5%	0.4% (absolute)	1.3%	0.0%	2:1	87%

**Table 17-2 Sensitivity of sample size (integers) to variations in SD and power**

#subjects in total	SD=1.1	SD=1.2	SD=1.3	SD=1.4
Power = 80%	270	321	375	435
Power = 85%	309	366	429	498
Power = 87%	327	390	456	528
Power = 90%	360	429	504	582

From [Table 17-2](#) it is seen that the primary objective will be met with at least 87% power with 456 subjects assuming a SD of 1.3%.

As this is a non-inferiority trial sample size will be determined such that the anticipated power is at least 87% in the evaluation of the PP analysis set. In previous phase 3 trials in type 2 diabetes treated with insulin 5-25% of the randomised subjects were excluded from the PP analysis set. The number of excluded subjects was dependent on the trial design. In this trial an estimate of 15% will be used and sample size is ceiled in the FAS to have integer sample size for each group that adheres exactly to the group allocation weights (2:1). Hence the total number of subject to be randomised must be 537 subjects in order to have at least 87% power in the evaluation of the PP analysis set ([Table 17-3](#)).

**Table 17–3 Anticipated number of subjects in FAS and PP analysis set**

	IDegAsp 30 BID	BIAsp 30 BID	Total
Number of subjects in the FAS	358	179	537
Number of subjects in the PP analysis set	304	152	456

## 17.2 Definition of analysis sets

- Full Analysis Set (FAS): includes all randomised subjects. In exceptional cases subjects from the FAS may be eliminated. In such cases the elimination will be justified and documented. The statistical evaluation of the FAS will follow the intention -to-treat (ITT) principle and subjects will contribute to the evaluation “as randomised”.
- The Per-Protocol analysis set will consist of all subjects in the Full Analysis Set who fulfils the following criteria:
  - Have not violated any inclusion criteria
  - Have not fulfilled any exclusion criteria
  - Have a non-missing HbA1c at screening or randomisation
  - Have at least one non-missing HbA1c after 12 weeks of exposure
  - Have at least 12 weeks of exposureSubjects will contribute to the evaluation “as treated”.
- Safety Analysis Set: includes all subjects receiving at least one dose of the investigational product or its comparator. Subjects in the safety set will contribute to the evaluation “as treated”.

Randomised subjects who are lost to follow up and where no exposure information of the investigational product or its comparator is available after randomisation will be handled as unexposed. The OADs that the subjects are included on and will stay on throughout the trial are concomitant medications and regarded as non-investigational products.

Before data are released for statistical analysis, a review of all data will take place to ensure a sufficient data quality and to ensure the planned statistical analyses are applicable. Any data decisions e.g. classification of anti-diabetic treatment not foreseen in the protocol, will be documented before database lock.

### 17.3 Primary endpoint

The primary endpoint is change from baseline in HbA1c (%) after 26 weeks of treatment

#### Statistical analysis

Change from baseline in HbA1c after 26 weeks of treatments will be analysed using an Analysis of Variance (ANOVA) method with treatment, anti-diabetic therapy at screening and sex as fixed factors, and age and baseline HbA1c as covariates. The anti-diabetic therapy at screening is a factor with the following four levels:

1. Basal insulin regimen without metformin
2. Basal insulin regimen with metformin
3. Premix/self-mix regimen without metformin
4. Premix/self-mix regimen with metformin

The model will be fitted to all the data simultaneously (all treatment groups) and from this model the relevant treatment differences will be estimated.

Non-inferiority will be considered confirmed if the upper bound of the two-sided 95% confidence interval is below or equal to 0.4% or equivalent if the p-value for the one-sided test of

$H_0: D > 0.4\%$  against  $H_A: D \leq 0.4\%$ ,

is less than or equal to 2.5%, where D is the mean treatment difference (investigational product minus comparator)

If non-inferiority is confirmed the superiority of the investigational product over comparator will be investigated. Superiority will be considered confirmed if the upper bound of the two-sided 95% confidence interval, which is calculated using the FAS, is below 0%. The PP analysis is considered supportive here.

#### Sensitivity analysis

The primary efficacy analysis will be repeated on the PP analysis set and the set of all completed subjects as sensitivity analyses.

The following sensitivity analyses will be performed using the FAS only.

All observed HbA1c measurements available post randomisation at scheduled measurement times will also be analysed in a linear mixed model using an unstructured residual covariance matrix (if possible), and with treatment, time, interaction between treatment and time, anti-diabetic treatment at screening and sex as fixed effects and age and baseline HbA1c as covariates.

This approach relies on the assumption that data are missing at random (MAR) according to the taxonomy defined by Rubin. The results will be compared to the results of the LOCF method for dealing with missing data. Any marked difference concerning treatment differences between the MAR and LOCF approach will be commented upon in the CTR.

Change in HbA1c from baseline will also be analysed using a model with only treatment as fixed factor and baseline HbA1c as covariate to assess the sensitivity of the results to inclusion/exclusion of fixed factors and covariates.

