## 11 Randomisation procedure

Randomisation will be carried out in a (2:1) manner using an IWRS to randomise subjects into the treatment groups: IDegAsp 30 BID or BIAsp 30 BID both in combination with or without metformin.

The treatment is open labelled.

Treatment will be allocated using centralised IWRS. It is important to dispense the exact allocated DUNs to a subject.

It is important for the sites only to dispense medication allocated by the IWRS in order to:

- Secure available stock at site to cover the drug supply needed for the enrolled subjects
- Ensure that no subjects are provided with trial drugs that will expire in between dispensing visits
- Ensure that it will be possible to perform drug accountability by using the IWRS

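### The mixed model that checks LOCF imposes one baseline-HbA1c slope on all visits; a baseline-by-time term would remove a small avoidable loss of precision and a possible bias

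*Protocol*

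**What the plan says.** The primary analysis (Protocol 17.3, SAP 2.3.1) is an ANOVA of change in HbA1c at week 26, with missing values filled by LOCF. It adjusts for treatment, anti-diabetic therapy, sex, age and baseline HbA1c.

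Under Sensitivity analysis (Protocol 17.3, SAP 2.3.2), all scheduled post-randomisation HbA1c values also go into a "linear mixed model using an unstructured residual covariance matrix (if possible"). The terms are "treatment, time, interaction between treatment and time, anti-diabetic treatment at screening and sex as fixed effects and age and baseline" HbA1c as covariates, worded identically in both documents. Baseline HbA1c is not crossed with time. The plan describes this model as relying on missing at random, and its result is to be set against LOCF: "Any marked difference concerning treatment differences between the MAR and LOCF approach will be commented upon in the CTR". There is no decision rule. The same section repeats the primary ANOVA on the per-protocol set and on completers.

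**The concern.** Subjects enter with HbA1c from 7.0 to 10.0% and are all titrated weekly to the same glucose target (Protocol 5.3, 6.2, Appendix A 3.2). Protocol 5.2 looks to weeks 12 and 16 to show when steady state is reached, so week 8 may come before it. HbA1c at week 8 may therefore still track baseline closely, and HbA1c at week 26 less so. Neither document explains why one slope should hold throughout.

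Two things follow if the slope does change. The week-26 contrast is adjusted with a slope that is not the week-26 slope, which costs precision. The implied week-26 value of a withdrawn subject with high or low baseline is also off. At stake is the comparison between the mixed model and LOCF, which is meant to show the effect of the missing-data method and nothing else. Withdrawal of 15% is expected (Protocol 6.1), about 80 of 537 subjects, in an open-label trial.

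**Working it through.** **1. The plan's own figures.** The inputs in Protocol 17.1 are a calculation "under the assumption of a one-sided test of size 2.5% and a zero mean treatment difference", the margin of 0.4%, and "an estimate for the standard deviation (SD) of 1.3% for" HbA1c. Allocation is 2:1 (Protocol 11). A noncentral-t calculation at 304/152 gives 87.1% power, matching the stated 87% with 456 subjects. Then 456/0.85 = 536.5, rounded up to 537 (358 + 179). These figures reproduce and the point does not touch them.

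**2. Which slope the model estimates.** The HbA1c row of the flow chart (columns partly broken in the text) reads as weeks 8, 12, 16, 20, 24 and 26. With complete data and unstructured covariance S given baseline, the common slope is w'g. Here g holds the visit-specific slopes and w = S⁻¹1/(1'S⁻¹1). Because S and g are not documented, I assumed values:

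- Correlation 0.92 per 4 weeks, constant residual SD: weight 0.44 on week 8 and 0.43 on week 26. Slopes of change on baseline moving linearly from -0.35 to -0.60 give a common slope of -0.475.
- Same correlation, residual SD rising from 0.8 to 1.0: week-8 weight 0.82, common slope -0.39.
- Same correlation, residual SD rising from 0.7 to 1.0: common slope -0.35.
- Compound symmetry, constant SD: each visit has weight 1/6 = 0.17.

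**3. Precision.** The relative rise in the week-26 variance is (common slope - week-26 slope)² × baseline variance / week-26 residual variance. The slopes in this table are for HbA1c level on baseline (slope of change plus 1; the gap is the same). I assumed baseline SD 0.8 and week-26 SD 1.0.

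| Correlation | Week 8 | Week 26 | Common | Variance rise | SE rise |
|---|---|---|---|---|---|
| Decaying (AR-type) | 0.81 | 0.50 | 0.76 | 0.26² × 0.64/0.84 = 5.2% | 2.5% |
| Intermediate | 0.68 | 0.47 | 0.61 | 0.14² × 0.64/0.859 = 1.5% | 0.7% |
| Compound symmetry | 0.54 | 0.62 | 0.58 | 0.04² × 0.64/0.754 = 0.1% | 0.1% |

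Over a wider grid the SE rise was 0-4.1% and the slope gap ran from -0.14 to +0.33. A steeper case has change slopes from -0.30 to -0.70 with residual SD from 0.7 to 1.0. It gives a gap of 0.395 and 0.395² × 0.64/1.0 = 10%, or about 5% in SE. For scale, at SD 1.3 and 358/179 the SE is 1.3 × √(1/358 + 1/179) = 0.119. The 95% half-width is 1.96 × 0.119 = 0.233, and 5% more is 0.245.

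**4. Bias with dropout.** I simulated 900,000 subjects per case with 14-15% dropout, true difference 0 and Monte Carlo SE about 0.002. Entries are the estimated differences under AR-type / intermediate / compound-symmetry correlation.

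| Dropout | As written | With baseline-by-time | LOCF |
|---|---|---|---|
| Random | 0.002 / -0.003 / 0.001 | 0.003 / -0.003 / 0.001 | 0.002 / -0.003 / 0.000 |
| On last HbA1c, alike in both arms | -0.002 / -0.002 / -0.002 | -0.002 / -0.001 / -0.003 | -0.001 / -0.001 / -0.004 |
| On last HbA1c, opposite by arm | 0.020 / 0.008 / -0.007 | -0.002 / -0.003 / -0.002 | 0.039 / 0.060 / 0.086 |
| On baseline, opposite by arm | 0.040 / 0.026 / -0.014 | 0.000 / 0.001 / -0.001 | 0.035 / 0.022 / -0.012 |

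In the last row the model as written agrees with LOCF while both are off. 0.040/0.4 = 10% of the margin. A separate run of that kind gave 0.034 for the model and 0.029 for LOCF. Swapping the arms would reverse the sign. In the third row the model as written is much closer to the truth than LOCF, so there it still does its job.

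At 537 subjects with dropout, the model SE without the term over that with it was about 1.03 (AR-type), 1.01 (intermediate) and 1.00 (compound symmetry).

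**The case against.** The strongest reply is that this is a specification preference. Non-inferiority rests on the LOCF ANOVA, the mixed model has no decision rule, and the loss is a few per cent of a standard error. All of that stands.

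The completer ANOVA also gives partial cover. It uses observed week-26 values, so its slope is specific to week 26, and it is valid when dropout depends only on covariates in the model. Simulated with baseline-dependent dropout in opposite directions by arm, it was unbiased (0.001). It does not have the same protection when dropout depends on post-baseline HbA1c, so it does not replace a well-specified mixed model.

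Without dropout, the two analyses would differ only by the slope gap times the chance imbalance in baseline. With an assumed baseline SD of 0.8, the SE of that imbalance is 0.8 × √(1/358 + 1/179) = 0.073. Even a gap of 0.33 shifts the estimate by about 0.33 × 0.073 = 0.024. That is unlikely to count as a marked difference.

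Three stronger readings are tempting, and the documents do not support them:

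- **That week 26 is in effect adjusted with the week-8 slope.** High correlation alone does not produce this. It needs correlation that decays with time and a residual SD that grows, and the documents give neither.
- **That the slope on baseline must steepen.** Titration makes a change plausible, but no figure fixes its size or even its sign.
- **That withdrawn subjects are mispredicted and the estimate is therefore biased.** The model also uses each withdrawn subject's observed HbA1c, and errors that are alike in both arms cancel in the difference.

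**Conclusion.** The point holds as a minor one. As written, the model imposes a single baseline slope, and nothing in either document justifies it. If the true slope changes over time, the common slope can lie anywhere between the early and late values. The cost is about 0-5% in the week-26 standard error. There is no bias when dropout is random or works alike in both arms.

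The 0.02-0.04 HbA1c % bias needs baseline-related dropout in opposite directions by arm, under decaying or intermediate correlation. That case was built to be extreme; under compound symmetry the bias was about 0.014 with the opposite sign. It matters mainly because LOCF errs the same way there, so agreement between the two would be false reassurance.

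All these sizes rest on assumed SDs, correlations, slopes and dropout mechanisms. The primary test, the sample size and the completer analysis are untouched.

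**What to change.** In Protocol 17.3 and SAP 2.3.2, add a baseline HbA1c-by-time interaction to the mixed model, or state that it is left out on purpose and why. With six post-randomisation HbA1c visits this costs 6 - 1 = 5 parameters against 537 subjects. It needs no new data and leaves the confirmatory analysis as it is. Therapy-by-time (3 × 5 = 15 more parameters) is optional.

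The change should not be described as making the adjustment identical to the primary ANOVA. Age and sex would still have common effects across visits, and the ANOVA's own slope is estimated partly from LOCF values. SAP 1.2 already requires changes of method to be reported with the reason in the clinical trial report.

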## **17.4 Secondary endpoints**

### **17.4.1 Confirmatory secondary endpoints**

Provided that non-inferiority is confirmed for the primary endpoint, a number of confirmatory secondary endpoints will be tested to confirm superiority of the investigational product over the comparator.

The confirmatory secondary endpoints are given below together with the direction of the test for superiority. The order of the endpoints defines the testing sequence.

1. Change from baseline in FPG after 26 weeks of treatment (analysed at central laboratory)
  - Superiority is considered confirmed if the 95% confidence interval for the treatment difference (investigational product minus comparator) is entirely below zero
2. Number of treatment emergent nocturnal confirmed hypoglycaemic episodes
  - Superiority is considered confirmed if the 95% confidence interval for the relative risk (investigational product / comparator) is entirely below one
3. Number of treatment emergent confirmed hypoglycaemic episodes
  - Superiority is considered confirmed if the 95% confidence interval for the relative risk (investigational product / comparator) is entirely below one
4. Change from baseline in body weight after 26 weeks of treatment
  - Superiority is considered confirmed if the 95% confidence interval for the treatment difference (investigational product minus comparator) is entirely below zero
5. Responder without hypoglycaemic episodes (HbA1c <7.0% after 26 weeks of treatment and no confirmed episodes during the last 12 weeks of treatment or within 7 days after the last randomised treatment including only subjects exposed for at least 12 weeks)
  - Superiority is considered confirmed if the 95% confidence interval for the odds ratio (investigational product / comparator) is entirely above one

### **Change from baseline in FPG**

Change from baseline in FPG after 26 weeks of treatment will be analysed using an ANOVA method with treatment, anti-diabetic therapy at screening and sex as fixed factors, and age and baseline FPG as covariates.

### **Number of treatment emergent confirmed hypoglycaemic episodes**

A hypoglycaemic episode is defined as treatment emergent if the onset of the episode is on or after the first day of exposure to randomised treatment and no later than 7 days after the last day of randomised treatment.

The number of confirmed hypoglycaemic episodes will be analysed using a negative binomial regression model with a log-link function and the logarithm of the time period in which a hypoglycaemic episode is considered treatment emergent as offset. The model will include treatment, anti-diabetic therapy at screening and sex as fixed factors, and age as covariate.

### **Number of treatment emergent nocturnal confirmed hypoglycaemic episodes**

A hypoglycaemic episode that has time of onset between 00:01 and 05:59 a.m. (both included) will be considered nocturnal.

The number of treatment emergent nocturnal confirmed hypoglycaemic episodes will be analysed using a negative binomial regression model with a log-link function and the logarithm of the time period in which a hypoglycaemic episode is considered treatment emergent as offset. The model will include treatment, anti-diabetic therapy at screening and sex as fixed factors and age as covariate.

### **Change from baseline in body weight**

Body weight is assessed at trial site. Change from baseline in body weight after 26 weeks of treatment will be analysed using an ANOVA method with treatment, anti-diabetic therapy at screening and sex as fixed factors, and age and baseline body weight as covariates.

### **Responder without hypoglycaemic episodes**

Responder without hypoglycaemic episodes is a dichotomous endpoint (responder/non-responder) that is defined based on whether a subject has met the ADA HbA1c target (< 7%) after 26 weeks of treatment without treatment emergent confirmed hypoglycaemic episodes during the last 12 weeks of treatment or within 7 days after last randomised treatment. The endpoint will only be defined for subjects that have been exposed to the investigational product or its comparator for at least 12 weeks.

Responder analysis will be based on a logistic regression model using treatment, anti-diabetic therapy at screening and sex as fixed factors, and age and baseline HbA1c as covariates.

## **17.4.2 Supportive secondary endpoints**

### **17.4.2.1 Efficacy**

The timing of assessments is outlined in the trial flow chart.

#### **HbA1c responder endpoints**

Two dichotomous endpoints (responder/non-responder) will be defined based on whether a subject has met the ADA HbA1c target (HbA1c < 7.0%) and the International Diabetes Federation (IDF) HbA1c target (HbA1c ≤ 6.5%) after 26 weeks of treatment.

Additional dichotomous endpoints will be defined based on whether those treatment targets after 26 weeks of treatment are achieved without hypoglycaemic episodes in the last 12 weeks of treatment or within 7 days after last randomised treatment considering confirmed episodes and severe episodes only. These endpoints will only be defined for subjects that have been exposed for at least 12 weeks.

The responder endpoints will be analysed separately based on a logistic regression model using treatment, anti-diabetic therapy at screening and sex as fixed factors, and age and baseline HbA1c as covariates.

#### **Self measured plasma glucose**

Self-measured plasma glucose will be measured in terms of the 9-point profiles (SMPG) and glucose measurements used for insulin dose adjustments.

#### ***9-point profile (SMPG) after 26 weeks of treatment***

A 9-point profile (SMPG) will include measurements before and 90 minutes after start of breakfast, lunch and main evening meal, measurements prior to bedtime and at 4 a.m., and one before breakfast the following day.

The endpoints from the 9-point profiles (SMPG) will be:

- 9-point profile (SMPG)
- Mean of the 9-point profile (SMPG)
- Fluctuation in the 9-point profile (SMPG)
- Prandial plasma glucose (PG) increments

The mean of 9-point profile (SMPG) is defined as the area under the profile divided by the measurement time and is calculated using the trapezoidal method. The fluctuation in the 9-point profile (SMPG) is defined as

$$\frac{1}{T} \int_0^T |PG(t) - \overline{PG}| dt$$

where  $T$ ,  $PG(t)$  and  $\overline{PG}$  denotes the length of the profile, the PG value at time  $t$  and the mean of the profile, respectively.

Prandial PG increment for each meal will be derived from the 9-point profile (SMPG) as the difference between PG values available 90 minutes after meal and before meal. Mean prandial PG increment over all meals will be derived as the mean of all available meal increments.

A mixed effect model will be fitted to the 9-point profile (SMPG) data. The model will include treatment, time, interaction between treatment and time, anti-diabetic therapy at screening and sex as fixed factors, age and the values from the profile at baseline as covariates and subject as random effect. From the model, mean profile by treatment and relevant treatment differences will be estimated and explored.

Mean and fluctuation in the 9-point profile (SMPG) and prandial PG increment endpoints will be analysed separately using an ANOVA method with treatment, anti-diabetic therapy at screening and sex as fixed factors, and age and the relevant baseline value as covariates. Fluctuation in the 9-point profile (SMPG) will be logarithm transformed before analysed.

